6.8.9. Surgery

Caution is advised for any surgical procedures during the study. The appropriate interval of time between surgery and PF-07265028 required to minimize the risk of impaired wound healing and bleeding has not been determined. Stopping PF-07265028 is recommended at least 7 days prior to surgery. Postoperatively, the decision to reinitiate PF-07265028 treatment should be based on a clinical assessment of satisfactory wound healing and recovery from surgery.

6.8.10. Radiotherapy

Palliative radiotherapy to specific sites of disease will be permitted if considered medically necessary by the treating physician. All attempts will be made to rule out progressive disease in the event of increased localized pain. Palliative radiotherapy to baseline target lesions should be avoided.

6.8.11. Rescue Medicine

There is no rescue therapy to reverse the AEs observed with PF-07265028; standard medical supportive care must be provided to manage the AEs.

The study site will supply rescue medication that will be obtained locally.

6.8.12. COVID-19 Vaccines

COVID-19 vaccines with authorization/approval are considered concomitant medications and standard AE collection and reporting processes should be followed. The timing of vaccine dosing relative to the dosing of study medications is at the discretion of the investigator although, if applicable, it is best to avoid the DLT observation period.

7. DISCONTINUATION OF STUDY INTERVENTION AND PARTICIPANT DISCONTINUATION/WITHDRAWAL

7.1. Discontinuation of Study Intervention

It may be necessary for a participant to permanently discontinue study intervention. Reasons for permanent discontinuation of study intervention may include the following:

- Disease progression;
- Lack of clinical benefit;
- Global deterioration of health status requiring discontinuation;
- Unacceptable toxicity;
- Pregnancy;
- Significant protocol violation;
- Lost to follow-up;
- Participant refused further treatment;
- Study terminated by sponsor;
- Death.

Note that discontinuation of study intervention does not represent withdrawal from the study.

If study intervention is permanently discontinued, the participant will remain in the study to be evaluated for safety up to 90 days (see [Section 8.2.9](#)). See the [SoA Table 1](#) for data to be collected at the time of discontinuation of study intervention and follow-up for any further evaluations that need to be completed.

In the event of discontinuation of study intervention, it must be documented on the appropriate CRF/in the medical records whether the participant is discontinuing further receipt of study intervention or also from study procedures, posttreatment study follow-up, and/or future collection of additional information.

Follow-Up:

Follow-up at 30 days (± 3 days) after discontinuation of study intervention, participants will return to the site for a safety follow up visit (see [SoA Table 1](#) and [Section 8.2.9](#)). Subsequent follow-up is required at 60 and 90 days (± 7 days) and may be a telephone follow-up. The investigator may conduct these follow-up visits in clinic if any concerns are noted during the remote contact. Participants continuing to experience treatment-related AEs at this point following discontinuation of treatment will continue to be followed at least every 4 weeks until resolution or determination, in the clinical judgment of the investigator, that no further improvement is expected.

7.1.1. Request to Continue Treatment

Participants with radiological progression per RECIST will be permitted to continue on study treatment while PD is confirmed, 4 or more weeks later as per irRECIST if the investigator believes that it is in the best interest of the participant. Participants who have confirmed progression per irRECIST may continue on therapy if, after discussion with the sponsor, the investigator considers that the participant is deriving clinical benefit from treatment; participants with rapid progression or sites of disease adjacent to or invading major blood vessels are not eligible for treatment beyond progression

Criteria that must be met to ensure that participants are not exposed to unreasonable risks by continued use of the investigational agent in spite of progression of disease may include the following:

- Absence of symptoms and signs indicating clinically significant progression of disease.
- No decline in ECOG performance status.
- Absence of symptomatic rapid disease progression requiring urgent medical intervention (eg, symptomatic pleural effusion, spinal cord compression).

At the time of radiographic progression of disease, obtain the re-consent of participants using a written informed consent document that details all FDA-approved therapy, and potential clinical benefit, that the participant may be foregoing in order to continue receiving the study intervention.

7.1.2. Potential Cases of Acute Kidney Injury

Abnormal values in SCr concurrent with presence or absence of increase in BUN/Urea that meet the criteria below, in the absence of other causes of kidney injury, are considered potential cases of acute kidney injury and should be considered important medical events.

An increase of ≥ 0.3 mg/dL (or ≥ 26.5 $\mu\text{mol/L}$) in SCr level relative to the participant's own baseline measurement should trigger another assessment of SCr as soon as practically feasible, preferably within 48 hours from awareness.

If the second assessment (after the first observations of ≥ 0.3 mg/dL [or ≥ 26.5 $\mu\text{mol/L}$] in SCr relative to the participant's own baseline measurement) is ≥ 0.4 mg/dL (or ≥ 35.4 $\mu\text{mol/L}$), the participant should be discontinued from the study and adequate, immediate, supportive measures taken to correct apparent acute kidney injury.

Participants should return to the investigator site and be evaluated as soon as possible, preferably within 48 hours from awareness of the second assessment confirming abnormal SCr result. This evaluation should include laboratory tests, detailed history, and physical assessment. In addition to repeating SCr, laboratory tests should include serum BUN/Urea, serum creatine kinase, and serum electrolytes (including at a minimum potassium, sodium, phosphate/phosphorus, magnesium and calcium), in addition to urinary dipstick, urine microscopic examination, and urinary indices. All cases confirmed on repeat testing as meeting the laboratory criteria for acute kidney injury, with no other cause(s) of laboratory abnormalities identified, should be considered potential cases of drug-induced kidney injury irrespective of availability of all the results of the investigations performed to determine etiology of the abnormal SCr.

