Grade 1 Grade 1 AST or ALT > ULN to 3.0 x ULN if baseline was normal, >1.5-3.0 x baseline if baseline was abnormal; and/or Total bilirubin > ULN to 1.5 x ULN if baseline was normal, >1.0-1.5 x baseline if baseline was abnormal	-Continue study treatment	-Continue liver function monitoring -If worsens: Treat as Grade 2 or 3 - 4.
Grade 2 AST or ALT >3.0 to ≤5 x ULN if baseline was normal, >3.0-5.0 x baseline if baseline was abnormal; and/or total bilirubin >1.5 to ≤3 x ULN if baseline was normal, >1.5-3.0 x baseline if baseline was abnormal	-Withhold study treatment -Increase frequency of monitoring to every 3 days.	-If returns to Grade ≤1: -Resume routine monitoring; resume study treatment. -If elevation persists >5 to 7 days or worsens: -Treat as Grade 3 to 4.
Grade 3 to 4 AST or ALT >5 x ULN if baseline was normal, >5.0 x baseline if baseline was abnormal; and/or total bilirubin >3 x ULN if baseline was normal, >3 x baseline if baseline was abnormal	-Permanently discontinue study treatment -Increase frequency of monitoring to every 1 to 2 days -1.0 to 2.0 mg/kg/day prednisone or equivalent -Add prophylactic antibiotics for opportunistic infections -Consult gastroenterologist/hepatologist -Consider obtaining MRI/CT scan of liver and liver biopsy if clinically warranted	-If returns to Grade ≤1: -Taper steroids over at least 1 month -If does not improve in >3 to 5 days, worsens or rebounds: -Add mycophenolate mofetil 1 gram (g) twice daily -If no response within an additional 3 to 5 days, consider other immunosuppressants per local guidelines.

090177e198aafefApproved\Approved On: 22-Nov-2021 20:52 (GMT)

Renal irAEs		
Grade of Creatinine Increased (NCI-CTCAE v5.0)	Initial Management	Follow-up Management
Grade 1 Creatinine increased > ULN to 1.5 x ULN	-Continue study treatment	-Continue renal function monitoring -If worsens: Treat as Grade 2 to 3 or 4.
Grade 2 to 3 Creatinine increased >1.5 and ≤6 x ULN	-Withhold study treatment -Increase frequency of monitoring to every 3 days -1.0 to 2.0 mg/kg/day prednisone or equivalent. -Add prophylactic antibiotics for opportunistic infections -Consider renal biopsy	-If returns to Grade ≤1: -Taper steroids over at least 1 month, and resume study treatment following steroids taper. -If worsens: -Treat as Grade 4.

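### The acute kidney injury rule in Protocol 7.1.2 prescribes a different action from the renal irAE table and Table 8 for the same creatinine rise, and names the study rather than study intervention as what ends

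*Protocol*

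**What the plan says.** Protocol 7.1.2 works in two steps. A rise of at least 0.3 mg/dL "in SCr level relative to the participant's own baseline measurement should trigger another assessment of SCr as soon as practically feasible". If the second assessment "is ≥ 0.4 mg/dL (or ≥ 35.4" µmol/L), then "the participant should be discontinued from the study and adequate, immediate, supportive measures taken to correct apparent acute kidney injury". The section next asks for a work-up: "Participants should return to the investigator site and be evaluated as soon as possible, preferably within 48 hours from awareness of the second assessment". It applies where no other cause of kidney injury is present, and confirmed cases "should be considered potential cases of drug-induced kidney injury irrespective of availability of all the results of the investigations performed".

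The renal table in Protocol 10.3.5 uses a different scale:

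- Grade 1, "Creatinine increased > ULN to 1.5 x ULN": treatment continues.
- Grade 2 to 3, "Creatinine increased >1.5 and ≤6 x ULN": treatment is withheld, then resumed after recovery and a steroid taper.
- Grade 4, above 6 x ULN: study treatment stops permanently.

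No renal row takes the participant out of the study.

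Table 8 in Protocol 6.5 covers toxicity related to PF-07265028. Nonhematologic Grade 1 and Grade 2 events continue at the same dose level.

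Protocol 7.1, the parent of 7.1.2, says: "Note that discontinuation of study intervention does not represent withdrawal from the study". It keeps a participant who stops drug in the study for safety up to 90 days, and has ongoing treatment-related AEs followed at least every 4 weeks.

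**The concern.** There are two separate conflicts.

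The first is about action. 7.1.2 measures an absolute change from the participant's own baseline, while the renal table measures a multiple of ULN. A modest rise can meet the 7.1.2 criterion and sit in the lowest renal grade, or in none. A site following 7.1.2 removes the participant; a site following the table continues or withholds treatment. Nothing tells the site which to follow.

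The second is about what ends. 7.1.2 sits under the section on stopping study intervention, and that section takes care to separate stopping drug from leaving the study. 7.1.2 nonetheless names the study, and then requires a return evaluation.

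At stake are consistent handling across sites of a possible drug-induced injury, and complete safety follow-up in the participants for whom it matters most.

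**Working it through.** **The plan's own figures.** With 1 mg/dL = 88.4 µmol/L, 0.3 x 88.4 = 26.52 and 0.4 x 88.4 = 35.36. Both stated conversions (26.5 and 35.4) reproduce.

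**Reading of the second criterion.** The text says that the second assessment is at least 0.4 mg/dL, without repeating that this is relative to baseline. As an absolute value it would not discriminate: a participant with a baseline of 0.8 mg/dL whose repeat had returned to 0.8 would still meet it. I read it as a rise over baseline. That is an interpretation.

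**Inputs.** The rise of 0.4 mg/dL is from 7.1.2. The grade limits of 1, 1.5 and 6 x ULN are from 10.3.5. ULN is not in the documents; I assume 1.0, 1.2 or 1.3 mg/dL.

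**Formulas.** For a rise of exactly 0.4:

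- no renal grade if baseline + 0.4 ≤ ULN, so baseline ≤ ULN − 0.4;
- at most Grade 1 if baseline + 0.4 ≤ 1.5 x ULN, so baseline ≤ 1.5 x ULN − 0.4.

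From a baseline of 0.8, Grade 4 needs a rise above 6 x ULN − 0.8.

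| Assumed ULN (mg/dL) | No grade: baseline up to | At most Grade 1: baseline up to | Grade 4 from baseline 0.8: rise above |
|---|---|---|---|
| 1.0 | 1.0 − 0.4 = 0.6 | 1.5 − 0.4 = 1.1 | 6.0 − 0.8 = 5.2 |
| 1.2 | 1.2 − 0.4 = 0.8 | 1.8 − 0.4 = 1.4 | 7.2 − 0.8 = 6.4 |
| 1.3 | 1.3 − 0.4 = 0.9 | 1.95 − 0.4 = 1.55 | 7.8 − 0.8 = 7.0 |

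**Three cases at ULN 1.2, each with a confirmed rise of 0.4 mg/dL.** All three meet the 7.1.2 criterion.

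- Baseline 0.8: value 1.2, ratio 1.2/1.2 = 1.00. This is not above ULN, so no renal row applies.
- Baseline 1.0: value 1.4, ratio 1.4/1.2 = 1.17. Grade 1: the renal table and Table 8 both continue treatment.
- Baseline 1.5: value 1.9, ratio 1.9/1.2 = 1.58. Grade 2 to 3: the renal table withholds; Table 8 continues if the event is graded 2.

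**Study or study intervention.** Under 7.1, stopping drug leads to safety follow-up within the study for up to 90 days. Under 7.2, leaving the study leads to an early discontinuation visit where possible and a pointer to the Schedule of Activities for follow-up. 8.3.1 adds that investigators need not actively look for AEs once participation has concluded. So the choice of noun in 7.1.2 affects which follow-up text a site reads as applying.

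**The case against.** **The rules have different scopes.** 7.1.2 is for injury with no other cause; the renal table is for immune-related events. This is fair, but the scopes overlap. 7.1.2 classes confirmed cases as potentially drug-induced before the cause has been worked out, and an immune-related rise on study drug can be one of them. Treating such a rise as drug-induced is my inference; the protocol does not say it. Section 6.5.1 describes when an unresolved toxicity moves to the irAE guidance, but does not rank that guidance against 7.1.2.

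**The sponsor would be consulted.** Section 8 has safety issues discussed with the sponsor at once to decide on continuing. This lowers the chance of divergent handling but does not remove the conflicting text.

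**Follow-up is largely protected.** A reader might infer that these participants would lose their safety follow-up. The documents do not support that. 7.2 points to follow-up assessments and bars further evaluation only where consent is withdrawn. 8.3.1 requires irAEs and treatment-related AEs to be collected for 90 days after the last dose, and 8.3.3 has each event pursued to resolution or stabilization. The placement of 7.1.2 under 7.1 also suggests loose wording. What stands is that follow-up could be reduced if a site reads the text literally together with the 8.3.1 line on concluded participation.

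**Tumor data.** A reader might also infer lost tumor assessments and biased safety data. Sections 8.1.1 and 8.2.8 place a tumor assessment at withdrawal from treatment. The RECIST appendix encourages documenting progression afterwards, but I find no later scheduled scan that leaving the study would remove. No mechanism or size of bias is shown.

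**Conclusion.** The inconsistency is real and should be corrected. Under 7.1.2 a confirmed 0.4 mg/dL rise means leaving the study. Under the renal table the same rise is ungraded, continued or withheld, depending on baseline and ULN, and Table 8 adds a third instruction. Across the assumed ULN range, baseline must exceed 1.1 to 1.55 mg/dL before such a rise leaves the continue band. From a baseline of 0.8 mg/dL, the only renal row with permanent discontinuation needs a rise above 5.2 to 7.0 mg/dL.

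This rests on the assumed ULN values, on reading 0.4 mg/dL as a rise over baseline, and on the overlap in scope. It would be too strong to say that the rules always give opposite actions, since at higher baselines the table withholds treatment. The conflict over what ends depends on none of the assumed creatinine values. Its consequence is limited to a possible reduction in follow-up. Which clinical rule is right is not judged here.

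**What to change.** 1. Reconcile 7.1.2 with the renal table in 10.3.5 and with Table 8, so that a given creatinine change leads to one stated action, or state which rule takes precedence and when.
2. Say explicitly in 7.1.2 whether the 0.4 mg/dL criterion is a rise over the participant's own baseline.
3. Reconcile 7.1.2 with 7.1: state whether study intervention or study participation ends, and which safety follow-up then applies.

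The choice of rule belongs to the sponsor. The cost is protocol wording only; the sample size and the planned analyses do not change.

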7.2. Participant Discontinuation/Withdrawal From the Study

A participant may withdraw from the study at any time at their own request. Reasons for discontinuation from the study may include:

- Refused further study procedures;
- Lost to follow-up;
- Death;
- Study terminated by sponsor;
- Withdrawal of consent;

- Investigator discretion.

At the time of discontinuing from the study, if possible, an early discontinuation visit should be conducted. See the [SoA Table 1](#) for assessments to be collected at the time of study discontinuation and follow-up and for any further evaluations that need to be completed.

If a participant withdraws from the study, he/she may request destruction of any remaining samples taken and not tested, and the investigator must document any such requests in the site study records and notify the sponsor accordingly.

If the participant withdraws from the study and also withdraws consent (see [Section 7.2.1](#)) for disclosure of future information, no further evaluations should be performed and no additional data should be collected. The sponsor may retain and continue to use any data collected before such withdrawal of consent.

7.2.1. Withdrawal of Consent

Participants who request to discontinue receipt of study intervention will remain in the study and must continue to be followed for protocol-specified follow-up procedures. The only exception to this is when a participant specifically withdraws consent for any further contact with him or her or persons previously authorized by the participant to provide this information. Participants should notify the investigator in writing of the decision to withdraw consent from future follow-up, whenever possible. The withdrawal of consent should be explained in detail in the medical records by the investigator, as to whether the withdrawal is only from further receipt of study intervention or also from study procedures and/or posttreatment study follow-up, and entered on the appropriate CRF page. In the event that vital status (whether the participant is alive or dead) is being measured, publicly available information should be used to determine vital status only as appropriately directed in accordance with local law.

7.3. Lost to Follow-Up

A participant will be considered lost to follow-up if he or she repeatedly fails to return for scheduled visits and is unable to be contacted by the study site.

The following actions must be taken if a participant fails to return to the clinic for/attend a required study visit:

- The site must attempt to contact the participant and reschedule the missed visit as soon as possible. Counsel the participant on the importance of maintaining the assigned visit schedule and ascertain whether the participant wishes to and/or should continue in the study.

- Before a participant is deemed lost to follow-up, the investigator or designee must make every effort to regain contact with the participant (where possible, 3 telephone calls and, if necessary, a certified letter to the participant's last known mailing address or local equivalent methods). These contact attempts should be documented in the participant's medical record.
- Should the participant continue to be unreachable, he/she will be considered to have withdrawn from the study.

8. STUDY ASSESSMENTS AND PROCEDURES

The investigator (or an appropriate delegate at the investigator site) must obtain a signed and dated ICD before performing any study-specific procedures.

Study procedures and their timing are summarized in the [SoA](#). Protocol waivers or exemptions are not allowed.

Safety issues should be discussed with the sponsor immediately upon occurrence or awareness to determine whether the participant should continue or discontinue study intervention.

Adherence to the study design requirements, including those specified in the [SoA](#), is essential and required for study conduct.

All screening evaluations must be completed and reviewed to confirm that potential participants meet all eligibility criteria. The investigator will maintain a screening log to record details of all participants screened and to confirm eligibility or record reasons for screening failure, as applicable.

Procedures conducted as part of the participant's routine clinical management (eg, blood count) and obtained before signing of the ICD may be utilized for screening or baseline purposes provided the procedures met the protocol-specified criteria and were performed within 14 days prior to signing of the ICD.

Every effort should be made to ensure that protocol-required tests and procedures are completed as described. However, it is anticipated that from time to time there may be circumstances outside the control of the investigator that may make it unfeasible to perform the test. In these cases, the investigator must take all steps necessary to ensure the safety and well-being of the participant. When a protocol-required test cannot be performed, the investigator will document the reason for the missed test and any corrective and preventive actions that he or she has taken to ensure that required processes are adhered to as soon as possible. The study team must be informed of these incidents in a timely manner. For samples being collected and shipped, detailed collection, processing, storage, and shipment instructions and contact information will be provided to the investigator site prior to initiation of the study.

All assessments are relative to start of study intervention (Cycle 1 Day 1). All assessments to be completed prior to administration of study intervention unless otherwise noted per study visit.

